4.2. Scientific Rationale for Study Design

PF-07260437 will be evaluated for the treatment of BrCa (and other malignancies, including uterine and OvCas). PF-07260437 addresses a significant unmet medical need for BrCa, as

its target B7-H4 is expressed in the majority of BrCas across all molecular subtypes (Leong et al, 2015). B7-H4, a member of the B7 family of proteins encoded by gene CCI [REDACTED], has been shown to have wide expression in BrCa along with other gynecologic malignancies. In addition, its limited expression in normal tissues makes B7-H4 an appealing tumor-associated antigen for targeting BrCas with CD3 bispecific molecules.

PF-07260437 demonstrated binding to a panel of tumor cell lines that express B7-H4 protein and human T lymphocytes that express CD3. The bispecific molecule exhibited concentration-dependent binding across a panel of cancer cell lines with varying levels of endogenous B7-H4 expression, as well as concentration-dependent binding on a panel of human donor T cells. In the presence of T cells, PF-07260437 elicited CTL responses against a panel of cancer cell lines expressing B7-H4. In the absence of T cells, PF-07260437 did not affect tumor cell growth. In vivo, PF-07260437 demonstrated B7-H4 expression-dependent antitumor activity against a panel of cell line xenograft and patient derived xenograft breast tumors grown in immune-compromised mice that were implanted with human T cells. Tumor growth inhibition following PF-07260437 treatment was dose dependent.

The objective of the biomarker assessments in this study is to provide insight into the pharmacological effects of PF-07260437 on the tumor and immune system. The assessments will contribute to confirming target engagement and measuring T-cell activation. Evaluation of target expression and modulation of immune signatures associated with the mechanism of PF-07260437 will require the collection of recent archival and/or de novo pre-treatment and on-treatment biopsies to establish the association between B7-H4 expression, biomarkers, and response parameters to PF-07260437 as described in the SOA and the Laboratory Manual. Biomarker assessments are intended to elucidate potential resistance mechanisms to PF-07260437 and identify participants who are most likely to benefit from treatment.

Banked biospecimens will be collected for exploratory/pharmacogenomic/genomic/biomarker analyses and retained in the BBS, which makes it possible to better understand the in vivo MoA and potential mechanisms of resistance of the investigational product and to seek explanations for differences in, for example, exposure, tolerability, safety, and/or efficacy not anticipated prior to the beginning of the study. These studies may help in the future development of PF-07260437 as a single agent and may provide information on tumor subtypes that may respond to the study intervention.

The PK analyses would serve to characterize the PK of PF-07260437 in human and its relationship with various factors (eg, body weight). Further identification of the PK-PD and exposure-response relationship for efficacy, safety, and the relevant biomarkers would guide the dose selection in subsequent trials.

4.2.1. Hormone Receptor (ER and/or PR) Positive BrCa

BrCa is the most common noncutaneous cancer in women with over 275,000 new cases expected to be diagnosed in the US in 2020. Approximately 70%-80% of new BrCas express the estrogen and/or progesterone receptor. Patients with advanced or metastatic HR-positive tumors benefit from hormonal therapy and CDK4/6 inhibitors. In addition, recently Alpelisib

was approved by FDA in treating advanced or metastatic HR+ HER2-, PIK3CA-mutant BrCa after an endocrine-based regimen. However, most patients develop resistance to these therapies, and all are associated with significant toxicities. Therefore, there remains an urgent need to identify new treatments.

4.2.2. Triple Negative BrCa

TNBC accounts for 15% of BrCas and is associated with poor long-term outcomes. Compared with other BrCa subtypes, TNBC affects younger women, is more frequent in black and Hispanic women and shows higher prevalence of germline BrCa mutation. TNBC is usually high grade, shows shorter time to relapse and higher risk for visceral metastases (Sharma, 2016).

The lack of ER, PR and HER2 expression precludes the use of targeted therapies in TNBC (Costa et al, 2019). Systemic therapy regimens for advanced or metastatic TNBC include taxanes as single agents or in combination with anthracyclines, platinum, or gemcitabine. A pooled analysis of Phase 3 trials in the first-line setting showed ORR of 23%, median PFS of 5.4 months and median OS of 17.5 months. Recently, FDA has granted accelerated approval to combine checkpoint inhibitors (Pembrolizumab and Atezolizumab) with chemotherapy as first-line therapy in PD-L1 positive advanced or metastatic TNBC. Most recently, FDA has granted regular approval to sacituzumab govitecan for patients with unresectable locally advanced or metastatic TNBC who have received 2 or more prior systemic therapies, at least one of them for metastatic disease. In addition, talazoparib and olaparib have been approved by FDA in treating germline BrCa mutant HER2-negative advanced or metastatic BrCa. However, none of these therapies is curative, and all are associated with significant toxicities. Therefore, new therapies for mTNBC are urgently needed.

Preclinically, PF-07260437 has demonstrated B7-H4 expression-dependent antitumor activity against HR+ HER2-, HER2+, and TNBC molecular subtype cell line xenograft and patient-derived xenograft breast tumors grown in immune-compromised mice that were implanted with human T cells. PF-07260437 treatment did not show antitumor efficacy in a model that does not express B7-H4.

These data provide rationale for exploring potential use of PF-07260437 in HR+ HER2- BrCa and TNBC.

4.2.3. Diversity of Study Population

Part 1 of the study will enroll adult participants with locally advanced or metastatic solid tumors including BrCa, OvCa and endometrial cancer. Adult participants with other B7-H4 expressing tumors may be included after discussion with and approval from sponsor. Part 2 will enroll participants with HR+ HER2- BrCa and TNBC with high B7-H4 expression and a cohort of 20 participants with HR+ HER2- BrCa or TNBC not selected for B7-H4 expression.

4.2.4. Dose Level Review

The determination of safety for each dose level with or without priming will be based on the discussion by the safety review team, comprised of the investigators and the sponsor. In addition, Pfizer will conduct unblinded data reviews during the course of the study for the purpose of safety assessment, facilitating PK/PD modeling or supporting clinical development.

4.2.5. Choice of Contraception/Barrier Requirements

Studies to evaluate the development toxicity of PF-07260437 have not been conducted. Therefore, the use of a highly effective method of contraception is required (see [Appendix 4](#)).

4.2.6. Collection of Retained Research Samples

Retained Research Samples will be collected and stored for further analyses which may, for example, provide greater understanding of the study intervention.

4.3. Justification for Dose

Doses presented are projected based on nonclinical data and may be modified based on emerging safety, tolerability, and PK data.

4.3.1. Starting Dose

4.3.1.1. Subcutaneous Administration

The starting dose will be 100 µg SC Q2W in 28-day cycles. The selection of the starting dose for this study was based on the MABEL in accordance with the ICH S9 Guidance, given that PF-07260437 is a bispecific T cell-engaging agent with immune agonistic properties. The 100 µg Q2W SC starting dose is predicted to result in minimal biological effect considering *in vitro* cytokine release and cytotoxicity experiments.

The *in vitro* biological activities for PF-07260437 were determined via cytotoxicity and cytokine release assays. The EC₅₀ value from the most sensitive *in vitro* assay was 0.062 nM. With a starting dose of 100 µg Q2W, the predicted PF-07260437 C_{max} after single dose, assuming 70% bioavailability from the SC route, is 9.2 ng/mL (0.063 nM), which is similar to the EC₅₀ (0.062 nM) of the most sensitive *in vitro* assay. Since C_{max} is believed to be associated with CRS and inflammatory responses, the blunted C_{max} offered by SC route is expected to increase the patient tolerability.

In addition, the proposed MABEL starting dose is lower compared to the 1/6 of HNSTD (1100 µg assuming 70 kg body weight) determined in the GLP 1-month toxicology study (0.3 mg/kg/week SC) in cynomolgus monkeys.

In summary, the proposed MABEL starting dose of 100 µg Q2W via the SC route is expected to result in minimal biological effect and to provide an adequate safety margin.

4.3.1.2. Alternative Intravenous Administration

If PK and safety data suggest that SC route is not a viable approach (eg, very low SC bioavailability or intolerable ISR), IV administration may also be evaluated in subsequent dose cohorts. To provide sufficient safety margin, the IV starting dose will be 20% of the highest safe/tolerable SC dose with assumption of 2.5 L of plasma volume for IV administration. For example, if the 300 µg SC dose level is deemed tolerable, the IV starting dose will be 60 µg. Notably, in the absence of any clinical safety data from SC dosing, the MABEL approach would yield an IV starting dose of 23 µg as the predicted C_{max} is similar to the EC₅₀ value from the most sensitive in vitro assay (0.062 nM). While it is not feasible to administer this IV dose of 23 µg based on the current formulation (with a lowest feasible IV dose of 45 µg), the IV route will not be potentially implemented until a SC dose level of \geq 300 µg. Therefore, the lowest possible IV dose is 60 µg, which is expected to provide similar exposure coverage with 300 µg at SC dose level 2 (see [Table 8](#)).

In addition, the HNSTD was 0.1 mg/kg/week from the IV arm of the GLP 1-month toxicity study in cynomolgus monkeys. This yielded an IV starting dose of 376 µg (1/6 HNSTD assuming 70 kg body weight in humans), which is higher than our provisional IV starting dose of 60 µg.

If IV route is evaluated, inpatient monitoring in a hospital for at least 48 hours after the first dose in Cycle 1 in dose escalation will be implemented as described in [Section 6.1](#). Additional inpatient observation for subsequent cycles beyond Cycle 1 may be considered based on the investigator's discretion and should be discussed with the sponsor.

4.3.2. Justification for Priming Dose Regimen

Priming dose approaches are commonly applied for T-cell engager bispecific modalities to initially sensitize the immune system at lower doses to reduce rate and grade of CRS ([Costa et al, 2019](#); [Garfall, 2020](#); [Madduri et al, 2020](#); [BLINCYTO \(blinatumomab\), 2021](#)). A priming dose approach may be initiated if a dose level induces \geq Grade 2 CRS (lasting for >24 hours) occurs in >1 participant despite treatment with tocilizumab and/or vasopressors. Initially, a single priming dose will be administered on C1D1 at 1 dose level below the dose level whereby the \geq Grade 2 CRS event was observed. The first full dose will be administered on C1D15 with a starting full dose that is 100% higher than the priming dose. Depending on the observed safety and tolerability profile, dose escalation on the full dose may still proceed with up to 3-fold increment from current full dose level. If \geq Grade 2 CRS is observed after the administration of full doses, a 2 step-up priming doses approach may also be implemented with the 2 priming doses administered on C1D1 and C1D8, respectively; both priming doses will be at dose levels where predicted probability of \geq Grade 2 CRS is $<20\%$.

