- **Priming Dose:** A priming dose approach in the next dose level may be initiated if a dose level induces \geq Grade 2 CRS (lasting for >24 hours) occurs in >1 participant despite treatment with tocilizumab and/or vasopressors. Initially, a single priming dose may be administered on C1D1 at 1 dose level below the dose level in which the recurrent \geq Grade 2 CRS event was observed. The first full dose will be administered on C1D15 with a starting full dose that is not higher than the full dose at which the recurrent \geq Grade 2 CRS event occurred. Depending on the observed safety and tolerability profile, dose escalation of the full dose may proceed with full dose increased by a maximum of 200%. If \geq Grade 2 CRS is observed after the administration of full doses, a 2 (or more) step-up priming dose approach may also be implemented (for example, 2 priming doses administered on C1D1 and C1D8, respectively); the initial priming dose will be at a dose level where predicted probability of \geq Grade 2 CRS is $<20\%$. In addition, dose finding without priming may still continue in parallel if MTD without priming has not been reached and RDE without priming has not been determined. Finally, additional priming dose strategies (eg, additional doses, different dosing levels and intervals) may be investigated based on emerging data.

All Part 1 participants in cohorts without a priming dose will be observed inpatient for at least 48 hours after the first SC dose (or the first IV dose, as applicable) on C1D1 and for at least 8 hours after the second SC dose (or the second IV dose, as applicable) on C1D15. Participants in cohorts with a priming dose will be observed inpatient for at least 24 hours after the first SC priming dose (or the first IV priming dose administration, as applicable) on C1D1 and 24 hours after the second (full) dose on C1D15 ([Table 7](#)). Modification of inpatient observation period might be allowed based on emerging safety data and will require discussion and agreement between investigator and sponsor.

- Participants who experience Grade ≥ 3 infusion-related adverse events (IV administration) or clinically significant cytokine release syndrome must be hospitalized for at least 24 hours for at least 4 doses subsequently (two cycles). If subsequent doses are tolerated without recurrence of Grade ≥ 3 infusion-related adverse events or clinically significant cytokine release syndrome, outpatient PF-

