4.3.5. Criteria for Dose Escalation

BLRM guided by the EWOC principle will be used in dose escalation. See Table 8 and [Appendix 9](#) for more details on the model. Using DLT data at all tested dose levels and prespecified prior distribution of model parameters, posterior probabilities of probability of having a DLT falling into 3 dosing intervals (underdosing, target dosing, overdosing) will be calculated for all dose levels. A dose may only be used for newly enrolled participants if the risk of excessive toxicity, ie, toxicity higher than 0.33 at that dose is less than 25%.

Typically, participants will be enrolled in cohorts of approximately 3 participants with at least 1 DLT evaluable participant in the first dose level in Part 1 without a priming dose and 2 DLT evaluable participants at all other dose levels in Part 1 with or without a priming dose. The maximum dose increases from the previous dose levels for regimen will be up to 200% (dose tripling from the previous dose level) but will be adjusted to no more than 100% (dose doubling from the previous dose level) following the observation of a DLT or if there are two Grade ≥ 2 clinically significant treatment-related AEs.

The provisional dose levels to be evaluated are listed in Table 8.

Table 8. Provisional Dose Levels in Dose-Escalation (SC Administration)

Dose Level ^a	Dose (μg)
-1 (if applicable)	60
1 ^b	100
2	300
3	900
≥ 4	Escalation to continue to MTD or desired pharmacologic activity

a. Intermediate doses may be evaluated based on clinical findings. Maximum 3-fold increment (dose tripling) at each dose level.
b. If the 100 μg SC Q2W dose is not tolerated, then a lower dose of 60 μg Q2W via SC route will be evaluated.

Dose escalation will stop when stopping criteria are met (see [Appendix 9](#)). According to the stopping criteria, at least 6 participants will be evaluated at the MTD.

Intra-participant dose escalation to the next dose level may be considered in consultation with the sponsor for participants(s) enrolled in the first dose level with the following conditions: 1) have cleared the DLT period in the dose escalation phase, 2) the next immediate higher dose level is safe in all participants with no DLTs, and 3) a period of a minimum of 2 cycles after the DLT observation period with the next immediate higher dose level has confirmed there are no clinically significant toxicities.

Stopping criteria:

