4.3.6.2. Non-Hematologic DLTs

Any treatment-related Grade ≥ 3 non-hematologic toxicity (see below for specifications applying to special circumstances):

- Hepatic toxicity:
 - Clinical events consistent with Hy's Law, ie,
 - ≥ 3 -fold elevations above the ULN of ALT or AST AND;
 - >2 x ULN elevation of serum total bilirubin without alternative explanation (eg, cholestasis or Gilbert's syndrome) AND;
 - Absence of initial findings of cholestasis (eg, elevated serum ALP) AND;
 - Absence of other reason(s) to explain the combination of increased AT and TBili, such as viral hepatitis A, B, or C; preexisting or acute liver disease; or another drug capable of causing the observed injury.
 - For participants with Grade 2 hepatic transaminase or alkaline phosphatase levels at baseline as a result of liver metastasis or bone metastasis, a hepatic transaminase or alkaline phosphatase level >10 times the ULN.
- Grade ≥ 3 fatigue lasting ≥ 5 days.
- Grade ≥ 3 nausea/vomiting or diarrhea lasting ≥ 3 days despite adequate antiemetic and other supportive care.
- Grade ≥ 3 CRS of any duration.
- Grade ≥ 3 QTcF prolongation (Repeat testing, re-evaluate by a qualified person, and correct reversible causes (such as electrolyte abnormalities or hypoxia). If, after

correction of any reversible causes, the Grade 3 QTcF prolongation persists, then the event should be considered a DLT).

- A treatment-related AE inducing a delay by >2 weeks in receiving the next scheduled cycle.
- Grade ≥ 3 anaphylaxis.
- Any Grade 5 AE (death) not clearly due to either the underlying disease or other etiologies.

In addition, irAEs that meet the following criteria will be considered as DLTs:

- Any Grade 4 irAE regardless of duration, any \geq Grade 4 colitis regardless of duration;
- Any Grade 3 or Grade 4 non-infectious pneumonitis regardless of duration;
- Any Grade 3 irAE, excluding colitis and pneumonitis, that does not start downgrading to \leq Grade 2 within 3 days after onset of the event despite maximal supportive care including systemic corticosteroids or dose not downgrade to \leq Grade 1 or baseline within 14 days;
- Any Grade 2 pneumonitis that does not resolve to \leq Grade 1 within 3 days of the initiation of maximal supportive care.

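### Section 4.3.2 sets the first full dose after priming at twice the priming dose, which exceeds the Section 4.1 cap when adjacent dose levels are less than two-fold apart

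*Protocol*

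**What the plan says.** Sections 4.1 and 4.3.2 of the protocol describe the same event. A dose level produces Grade 2 or higher CRS lasting more than 24 hours in more than one participant despite tocilizumab and/or vasopressors. A single priming dose may then be given on C1D1, one level below the level that caused the CRS, with the first full dose on C1D15.

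They differ on the size of that first full dose:

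- Section 4.1 (Priming Dose): "with a starting full dose that is not higher than the full dose at which the recurrent" CRS event occurred.
- Section 4.3.2: "with a starting full dose that is 100% higher than the priming dose". No upper limit is stated.

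Section 4.3.5 determines how far apart the levels can be. Table 8 lists 60 (level −1), 100, 300 and 900 µg. Its footnotes add that "Intermediate doses may be evaluated based on clinical findings", with tripling as the maximum step, and that 60 µg is used if the 100 µg "dose is not tolerated, then a lower dose of 60" µg. The permitted increment "will be adjusted to no more than 100% (dose doubling from the previous dose level) following the observation of a DLT" or two Grade 2 or higher clinically significant related AEs.

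Neither the synopsis nor SAP Section 2.2 contains a full-dose rule that would decide between the two sections.

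**The concern.** Section 4.1 places its cap among the measures for limiting participant risk from CRS and immune-related events. Section 4.3.2 omits it. Where levels are close together, doubling the priming dose goes past the dose that caused the problem, so a step intended to reduce CRS could prescribe more drug than the dose that provoked it, in a first-in-human study of a T-cell engager. The overshoot grows as the steps become smaller, and small steps are what a cautious team would choose after toxicity.

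**Working it through.** **Inputs.** P is the priming dose and D the full dose at which recurrent CRS occurred. Both sections place P one level below D. Let r = D/P, with r at most 3 (Table 8).

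**Formula.** Section 4.3.2 gives F = 2P. Section 4.1 requires F ≤ D = rP. The rules are compatible if and only if r ≥ 2. F relative to the cap is 2P/(rP) − 1 = 2/r − 1.

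**Check on the planned steps.** 100 to 300 and 300 to 900 µg are each +200%, as the tripling rule says.

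| P / D (µg) | r | F = 2P | Cap D | F vs cap | Status |
|---|---|---|---|---|---|
| 100 / 300 | 3 | 200 | 300 | −33% | Table 8 |
| 300 / 900 | 3 | 600 | 900 | −33% | Table 8 |
| 60 / 100 | 1.67 | 120 | 100 | +20% | Table 8, remote |
| 300 / 600 | 2 | 600 | 600 | 0% | illustrative |
| 300 / 450 | 1.5 | 600 | 450 | +33% | illustrative |

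By the same formula a 75% increment (r = 1.75) gives +14% and a 25% increment (r = 1.25) gives +60%. The protocol names no 450 or 600 µg level. Once the limit of a doubling applies, Section 4.3.2 equals the cap at a full doubling and exceeds it at any smaller increment.

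**Would escalation with overdose control (EWOC) stop it?** Section 4.3.5 states: "A dose may only be used for newly enrolled participants if the risk of excessive toxicity", meaning a DLT rate above 0.33, is below 25%. That rule sees only DLTs. In Section 4.3.6.2 the CRS entry begins at Grade 3 ("CRS of any duration"). In Appendix 11, Grade 2 hypotension is the kind that does not need vasopressors. Grade 2 CRS treated with tocilizumab can therefore trigger priming without counting as a DLT, unless the discretionary clause in Section 4.3.6.3 is used.

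I computed the posterior under the Appendix 9 model and prior: (log α, log β) bivariate normal, means (logit p\*, 0), SDs 2 and 1, correlation 0. The documents give neither p\* nor d\*. I assumed p\* of 0.10, 0.15, 0.20, 0.25, 0.30 and 0.33, and d\* of 100, 300, 900 and 2700 µg, making 24 combinations.

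| DLT data | Dose tested | P(DLT rate > 0.33) below 0.25 |
|---|---|---|
| 0/3 at 100 µg | 120 µg | 24 of 24 (range 0.006–0.166) |
| 1/3 at 100 µg | 120 µg | 3 of 24 |
| 2/3 at 100 µg | 120 µg | 0 of 24 (range 0.63–0.89) |
| 0/3 at each of 100, 300, 450 µg | 600 µg | 24 of 24 (range 0.003–0.12) |
| 0/3, 1/3, 0/3 at 100, 300, 450 µg | 600 µg | 14 of 24 |
| 0/3, 0/3, 1/3 at 100, 300, 450 µg | 600 µg | 10 of 24 |

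If the triggering CRS is Grade 2 and there has been no DLT, EWOC leaves the higher dose open under every prior tried. Once DLTs occur, it often or always closes it.

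**The case against.** The strongest reply is that no planned step is affected. The one named pair below two-fold, 60/100 µg, needs recurrent CRS at 100 µg, where the "starting dose is predicted to result in minimal biological effect", and the stated response to intolerance there is to evaluate 60 µg. All other pairs are hypothetical. Reaching one through the doubling limit requires earlier toxicity, then a chosen increment smaller than a doubling, then recurrent CRS at that new level, then a decision to use priming, which is optional. This stands, and it limits how serious the point is. Intermediate doses are a shorter route, but also discretionary.

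Second, Section 4.1 lets unprimed dose finding continue in parallel, and its increment limit after such events is up to 2D. Since P is below D, 2P is always below 2D: 120 against 200 µg for 60/100, and 600 against 900 µg for 300/450. The disputed dose therefore never exceeds the increment ceiling for unprimed participants. That is correct and tempers the safety argument, but it does not say which rule applies to primed participants, for whom Section 4.1 chose a tighter limit.

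Third, the Section 4.1 cap is explicit, Section 4.3 says doses may be modified on emerging data, the sponsor confirms each Part 1 dose level in writing (Section 6.3.1), and the Dose Level Review Committee reviews all data (Section 4.3.8). These are real safeguards. A careful team would probably use the lower of the two doses. The protocol does not tell them to.

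Fourth, the EWOC check uses the unprimed model, whereas primed cohorts use a meta-analytic-predictive prior whose values are not given. That limit stands: the check shows that EWOC cannot be relied on to replace the cap, not what the primed model would return.

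**Conclusion.** The concern holds. The two sections give incompatible first full doses whenever adjacent levels are less than two-fold apart, and nothing in the protocol or SAP says which prevails. The excess is 2/r − 1: +20% for 60/100 µg, the only such pair that Table 8 names and a remote one, and +33% for an illustrative 50% step. There is no conflict at the planned 100/300 and 300/900 µg steps. The dose arithmetic rests only on the protocol's own rules. The statement about EWOC also depends on assumed p\* and d\* and on the unprimed prior. This should be corrected at the next amendment; it is not a defect in the escalation as currently planned.

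**What to change.** In Section 4.3.2, extend the sentence on the first full dose so that it is also no higher than the full dose at which the recurrent Grade 2 or higher CRS occurred, as Section 4.1 already requires. The first full dose then becomes min(2P, D). Leave the full-dose rule in Section 4.1 unchanged; it does not need the doubling rule added.

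The cost is one clause. At steps of two-fold or more nothing changes (200 and 600 µg stay as they are) and no cohort is added. Below two-fold the first full dose falls to the cap: 100 instead of 120 µg (20/120 = 17% lower), or 450 instead of 600 µg in the illustration (150/600 = 25% lower). Later escalation of the full dose by up to 200% remains available under Section 4.1.
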